Appendix 3: WHO-DD Preferred Terms for Antibiotics and Anti-Pseudomonal Antibiotics

COMMON ANTIBIOTICS WHO PT	ANTI-PSEUDOMONAL
ADENOMYCIN	
ADICILLIN	
ALATROFLOXACIN	
AMIKACIN	Y
AMIKACIN SULFATE	Y
AMOXICILLIN	
AMOXICILLIN SODIUM;CLAVULANATE POTASSIUM	
AMOXICILLIN TRIHYDRATE	
AMOXICILLIN TRIHYDRATE;CLAVULANATE POTASSIUM	
AMOXICILLIN;CLAVULANATE POTASSIUM	
AMOXICILLIN;CLAVULANIC ACID	
AMPHOTERICIN B	
AMPICILLIN;SULBACTAM	
ASPOXICILLIN	
ASTROMICIN	
AVAROFLOXACIN	
AVIBACTAM	Y
AZIDOCILLIN	
AZITHROMYCIN	Y
AZITHROMYCIN DIHYDRATE	Y
AZTREONAM	Y
BACAMPICILLIN	
BALOFLOXACIN	
BEKANAMYCIN	
BENZYL PENICILLIN	
BENZYL PENICILLIN SODIUM	
BRODIMOPRIM	
CAFROLYCYCLINE	
CARBENICILLIN	
CARBOMYCIN A	
CARINDACILLIN	
CARUMONAM	

CONFIDENTIAL

Sponsor:	Zambon S.p.A.	Protocol Number:	Z7224L02
----------	---------------	------------------	----------

COMMON ANTIBIOTICS WHO PT	ANTI-PSEUDOMONAL
CEFACETRILE	
CEFACTOR	Y
CEFADROXIL	Y
CEFALEXIN	Y
CEFALOGLYCIN	
CEFALORIDINE	
CEFALOTIN	
CEFAMANDOLE	
CEFAPIRIN	
CEFATHIAMIDINE	
CEFATRIZINE	Y
CEFAZOLIN	Y
CEFAZOLIN SODIUM	Y
CEFEPIME	Y
CEFIXIME	Y
CEFRADINE	Y
CEFTAZIDIME	Y
CEFTAZIDIME/AVIBACTAM	Y
CEFTOLOZANE SULFATE;TAZOBACTAM SODIUM	Y
CEFTOLOZANE/TAZOBACTAM	Y
CEFTRIAZONE	Y
CEFTRIAZONE SODIUM	Y
CEFUROXIME	Y
CEFUROXIME AXETIL	Y
CHLORAMPHENICOL	
CIPROFLOXACIN	Y
CIPROFLOXACIN HYDROCHLORIDE	Y
CIPROFLOXACIN LACTATE	Y
CLARITHROMYCIN	Y
CLAVULANIC ACID	
CLINDAMYCIN	
CO-AMOXICLAV	
COLISTIMETHATE SODIUM	Y
COLISTIN	Y
COLISTIN SULFATE	Y
CO-TRIMOXAZOLE	
DORIPENEM	Y
DOXYCYCLINE	Y

CONFIDENTIAL

Sponsor:	Zambon S.p.A.	Protocol Number:	Z7224L02
----------	---------------	------------------	----------

COMMON ANTIBIOTICS WHO PT	ANTI-PSEUDOMONAL
DOXYCYCLINE HYDROCHLORIDE	Y
ERYTHROMYCIN	Y
FIDAXOMICIN	Y
FLUCLOXACILLIN	
FOSFOMYCIN	Y
FUSIDATE SODIUM	
GENTAMICIN	Y
IMIPENEM	Y
IMIPENEM/CILASTATIN	Y
LEVOFLOXACIN	Y
LINCOMYCIN HYDROCHLORIDE	
MEROPENEM	Y
MEROPENEM TRIHYDRATE	Y
METHENAMINE	
METHENAMINE HIPPURATE	
METRONIDAZOLE	
MOXIFLOXACIN	Y
MOXIFLOXACIN HYDROCHLORIDE	Y
NITROFURANTOIN	
OFLOXACIN	
PIPERACILLIN	Y
PIPERACILLIN SODIUM;TAZOBACTAM SODIUM	Y
PIPERACILLIN;TAZOBACTAM	Y
POLYMYXIN B	
ROXITHROMYCIN	Y
SULFAMETHOXAZOLE	
SULFAMETHOXAZOLE;TRIMETHOPRIM	
SULTAMICILLIN	
TAZOBACTAM	Y
TOBRAMYCIN	Y
TOBRAMYCIN SULFATE	Y
TRIMETHOPRIM	

CONFIDENTIAL

Z7224L02_SAP_v4_FINAL_08.02.2022

Final Audit Report

2022-04-08

Created:	2022-04-08
By:	PPD
Status:	Signed
Transaction ID:	CBJCHBCAABAAsB5gLhyJIPIPCdlPaFGyuXz9MfmG2OPL

"Z7224L02_SAP_v4_FINAL_08.02.2022" History

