4.6 Prior and Concomitant Medication

The incidence of prior and concomitant medications will be presented by therapeutic area according to the Anatomical Therapeutic Chemical (ATC) level 4 classification and preferred drug name, by treatment and overall for the mITT Population.

Prior medications are those that started and stopped before exposure to IMP; concomitant medications are all medications taken during the study period, including those started before but on going at first IMP dose.

Where a medication start/stop date is partially or fully missing, and it is unclear as to whether the medication is prior or concomitant, it will be assumed that it is concomitant.

Notes:

CONFIDENTIAL

Sponsor:	Zambon S.p.A.	Protocol Number:	Z7224L02
----------	---------------	------------------	----------

- Prior and concomitant medications are all medications collected in the eCRF forms Prior and Concomitant Medications and Systemic Antibiotic Therapy.
- Medications are coded using the World Health Organisation (WHO) Drug Dictionary, WHO-DD (please refer to the final Data Management Plan for the latest coding information);
- Only the number of subjects with medications (not the number of medications) will be presented;
- If a subject has multiple occurrences of a medication, the subject will be presented only once in the respective subject count;
- Prior and concomitant medications will be summarised in separate tables;
- Medications will be displayed in descending ATC text and drug name frequency overall and then alphabetically.

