In order to provide the best estimates of the median time to first exacerbation, a Weibull accelerated failure time model will be applied to the data using CCI. The same terms as fitted in the Cox regression analysis will be fitted in the Weibull analysis. From the Weibull analysis, estimates of the median time to first exacerbation plus 95% CI will be extracted for each randomised treatment arm along with the ratio of median times and its 95% CI and p-value.

The CCI endpoint will also be analysed in terms of subgroup 7, as explained in Section 4.1.5.

CCI *Analysis for the Effect of Concomitant Antibiotic Therapy*

A supportive analysis examining the impact of antibiotic use (by adding an additional covariate to the Cox proportional hazard regression model so that the hazard ratio is adjusted for this) will be conducted to determine if the use of antibiotics for conditions other than CCI has any impact on the CCI.

The list of medications coded to WHO-DD Preferred Terms for antibiotics and anti-pseudomonal antibiotics are included in Appendix 3. If any medication in the list has a related CCI, the response to the question CCI "?" on the CCI page for that CCI will then be checked to see whether or not the CCI in the opinion of the Investigator. If answered "No", the medication was not taken for a CCI and will be included as antibiotics used for conditions other than a CCI. Medications in the resulting list that do not have a related CCI will also be checked and included as antibiotics used for conditions other than a CCI.

Two additional tables will be presented:

CONFIDENTIAL

Sponsor:	Zambon S.p.A.	Protocol Number:	Z7224L02
----------	---------------	------------------	----------

- Supportive Cox proportional hazards analysis with use of any antibiotics for conditions other than a CCI (Yes/No) as an additional covariate.
- Supportive Cox proportional hazards analysis with use of any anti-pseudomonal antibiotics for conditions other than a protocol-defined pulmonary exacerbation (Yes/No) as an additional covariate.

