5.3.3 Section 14.2: Secondary

Table 14.2.2.1.1	CCI : Kaplan-Meier Estimates	(mITT Population)
Table 14.2.2.1.2	CCI : Kaplan-Meier Estimates	(PP Population)
Table 14.2.2.1.5	CCI : Weibull Accelerated Failure Time Model	(mITT Population)
Table 14.2.2.1.6	CCI : Weibull Accelerated Failure Time Model	(PP Population)
Table 14.2.2.2.1	CCI : Cox proportional hazard regression model	(mITT Population)
Table 14.2.2.2.2	CCI : Cox proportional hazard regression model	(PP Population)
Table 14.2.2.2.3	CCI : Cox proportional hazard regression model - CCI Analysis for the Effect of Concomitant Antibiotic Therapy	(mITT Population)

CONFIDENTIAL

Sponsor:	Zambon S.p.A.	Protocol Number:	Z7224L02
----------	---------------	------------------	----------

Table 14.2.2.2.4	CCI [REDACTED]: Cox proportional hazard regression model - CCI [REDACTED] Analysis for the Effect of Concomitant Anti-Pseudomonal Antibiotic Therapy	(mITT Population)
Table 14.2.2.3	CCI [REDACTED]: Kaplan-Meier Estimates by IMP Adherence	(mITT Population)
Table 14.2.2.5.1	CCI [REDACTED]: Domain Scores and Total Score Results and Change Versus Baseline	(mITT Population)
Table 14.2.2.5.2	CCI [REDACTED]: Domain Scores and Total Score Results and Change Versus Baseline	(PP Population)
Table 14.2.2.5.3	CCI [REDACTED]: Linear Mixed Model for Repeated Measures for Change from Baseline in Total Score	(mITT Population)
Table 14.2.2.5.4	CCI [REDACTED]: Linear Mixed Model for Repeated Measures for Change from Baseline in Total Score	(PP Population)
Table 14.2.2.6.1	CCI [REDACTED] Density: Results and Change from Baseline	(mITT Population)
Table 14.2.2.6.2	CCI [REDACTED] Density: Linear Mixed Model for Repeated Measures for Change from Baseline at Visit 3, Visit 7 and End of Treatment	(mITT Population)
Table 14.2.2.7.1	Severe CCI [REDACTED]: Mean Annual Rate by Negative Binomial Model	(mITT Population)
Table 14.2.2.7.2	Time to CCI [REDACTED] Exacerbation: Kaplan-Meier Estimates	(mITT Population)
Table 14.2.2.8.1	CCI [REDACTED] - CCI [REDACTED] Days: Summary Statistics	(mITT Population)
Table 14.2.2.8.2	CCI [REDACTED] CCI [REDACTED] Days: ANCOVA model	(mITT Population)
Table 14.2.2.9	CCI [REDACTED]	(mITT Population)
Table 14.2.2.10.1	CCI [REDACTED]	(mITT Population)
Table 14.2.2.10.2	CCI [REDACTED]: Mean Annual Rate by Negative Binomial Model	(mITT Population)
Table 14.2.2.11.1	CCI [REDACTED]: Domain Scores Results and Change Versus Baseline	(mITT Population)

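### The Appendix 3 drug list used to define antibiotic exposure in two supportive Cox analyses contains an antifungal, thins out after the letter C and sets no route limit, so it can misclassify users

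*SAP*

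**What the plan says.** SAP 4.7.6.1 plans a supportive analysis asking whether antibiotics used for other conditions affect its time-to-event endpoint. The selection rule starts from an appendix: "The list of medications coded to WHO-DD Preferred Terms for antibiotics and anti-pseudomonal antibiotics are included in Appendix 3".

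- A listed drug with a related record is checked against an Investigator question, and counts if the answer is No.
- Listed drugs without a related record "will also be checked and included as antibiotics used for conditions other than a" protocol-defined event.

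The result enters as one Yes/No term: "Supportive Cox proportional hazards analysis with use of any antibiotics for conditions other than a" protocol-defined exacerbation, with a second model for anti-pseudomonal antibiotics. SAP 5.3.3 assigns these to Tables 14.2.2.2.3 and 14.2.2.2.4 (the first titled "Analysis for the Effect of Concomitant Antibiotic Therapy"), both on the mITT population.

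The name column of Appendix 3 is headed "COMMON ANTIBIOTICS WHO PT". Its rows include "CEFTRIAZONE SODIUM" and "AMPHOTERICIN B". A second column marks anti-pseudomonal drugs with Y. Neither 4.7.6.1 nor the appendix mentions route. SAP 4.6 takes medications from both the Prior and Concomitant Medications form and the Systemic Antibiotic Therapy form, and summarises them "according to the Anatomical Therapeutic Chemical (ATC) level 4 classification and preferred drug name".

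**The concern.** A list used as a matching key has to be complete for the drugs of interest and has to leave out the others. Appendix 3 does neither on its face. The checking step does not repair this, because it works only on drugs already on the list.

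Two errors follow. A subject whose only other antibiotic is unlisted is coded No. A subject who used a listed drug as an eye drop, ear drop or cream can be coded Yes, as can one given the listed antifungal. Both errors make the Yes and No groups more alike. The stated purpose is to learn whether other antibiotics have any impact, so the covariate's own hazard ratio is a result of interest. Bias towards 1 would lean the table towards a finding of no impact.

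**Working it through.** The plan gives no figure to reproduce here. The check has two parts.

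**1. What the list contains.** Input: the rows of Appendix 3 as supplied.

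- 102 rows, of which 51 are marked Y.
- By first letter: A 21, B 6, C 41, so A to C = 21 + 6 + 41 = 68. The remainder is 102 − 68 = 34 rows for D to Z.
- 45 rows stand at or before CEFAZOLIN SODIUM (A 21 + B 6 + the first 18 C rows), leaving 57.
- Rare agents early in the alphabet are present (adicillin, avarofloxacin).
- No row exists for plain ampicillin (only the sulbactam combination), phenoxymethylpenicillin, cefotaxime, ertapenem, minocycline, tetracycline, norfloxacin, linezolid, vancomycin or rifampicin.
- AMPHOTERICIN B is listed, without the Y mark.
- CEFTRIAZONE, CEFTRIAZONE SODIUM and CEFACTOR appear, all marked Y. No row reads CEFTRIAXONE or CEFACLOR.
- Chloramphenicol, fusidate, ofloxacin, ciprofloxacin and tobramycin are listed. All have eye, ear or skin forms. By contrast, exclusion criterion 16 (Protocol 8.2.2) names intravenous, intramuscular, oral and inhaled routes.
- Azithromycin, erythromycin and clarithromycin are listed, although stable oral macrolide use is already a term in the same Cox model. The SAP does not say whether maintenance macrolide use also makes the new covariate Yes.

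**2. What misclassification would do.** The simulation is illustrative. From the documents: 287 subjects randomised (SAP 3.9), placebo rate 1.09 per year and a 35% treatment effect, taken as rate ratio 0.65 (Protocol Summary, Sample Size). Assumed, because the documents do not give them: 30% true users, a conditional covariate hazard ratio of 1.5 or 2.0, gamma heterogeneity between subjects, random censoring between 3 and 12 months, and errors unrelated to arm. Each setting had 300 runs. Shrinkage = 1 − ln(HR with misclassified covariate) / ln(HR with true covariate).

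| Assumed HR | Sensitivity / specificity | Covariate HR, true → misclassified | Shrinkage of log HR | Treatment HR, true → misclassified |
|---|---|---|---|---|
| 1.5 | 90% / 95% | 1.414 → 1.326 | 1 − 0.282/0.346 = 18% | 0.685 → 0.684 |
| 1.5 | 70% / 90% | 1.403 → 1.248 | 1 − 0.222/0.339 = 35% | 0.687 → 0.687 |
| 1.5 | 50% / 85% | 1.390 → 1.110 | 1 − 0.104/0.329 = 68% | 0.690 → 0.689 |
| 2.0 | 90% / 95% | 1.780 → 1.624 | 1 − 0.485/0.577 = 16% | 0.692 → 0.693 |
| 2.0 | 70% / 90% | 1.774 → 1.418 | 1 − 0.349/0.573 = 39% | 0.698 → 0.702 |
| 2.0 | 50% / 85% | 1.801 → 1.262 | 1 − 0.233/0.588 = 60% | 0.695 → 0.700 |

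A protective effect behaves the same way. With 20% or 35% users and a true marginal hazard ratio of about 0.65, the estimate was about 0.69 to 0.70 at 80% sensitivity and 97% specificity, about 0.75 at 80% and 92%, and about 0.77 to 0.78 at 60% and 92%.

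The covariate's hazard ratio moves towards 1 in every setting. The treatment hazard ratio moves by at most about 0.005, as expected when randomisation keeps covariate and arm nearly independent.

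**The case against.** The case for leaving the list alone has several parts.

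- **Spelling.** A reader might infer that the list contains names that do not exist, so that coded ceftriaxone and cefaclor match nothing. The documents do not establish that. The text was machine-read from PDF, and the doubtful entries are one letter away from the familiar names and sit where those names would sort. Equally, X is read correctly in neighbouring rows such as CEFUROXIME AXETIL, so a typing error in the source is possible. Only the original file and the dictionary can settle it; the action is to check.
- **Combination formats.** Some combinations use a slash and others a semicolon. Whether slash entries fail to match cannot be judged without the WHO-DD, so no weight is placed on this.
- **Omissions.** An absent drug matters only if a subject took it and it was coded to an unlisted term. Salt-specific rows (meropenem trihydrate, methenamine hippurate) suggest that part of the list may come from coded trial data, although the SAP does not say so. The column is also headed as common antibiotics. This is fair as to size. It does not explain why rare agents are listed while vancomycin and linezolid are not.
- **Checking step.** Listed drugs are checked, and the protocol records reason for use. That could remove some topical use, but the SAP gives no criterion for it, and the step cannot recover unlisted drugs.
- **Treatment estimate.** A reader might infer that the adjusted treatment hazard ratio is distorted. The simulation does not support this.

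What stands is a selection rule that can misclassify exposure in either direction.

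**Conclusion.** The concern holds as a weakness of specification in two supportive tables, 14.2.2.2.3 and 14.2.2.2.4, since the anti-pseudomonal flag is applied to the same rows. As written, the rule can code systemic antibiotic users as No and users of topical products or an antifungal as Yes, which would bias the covariate's own hazard ratio towards 1.

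The size in this trial is unknown. The shrinkage of 16% to 68% in the table follows from assumed sensitivity, specificity, prevalence and effect, with errors unrelated to arm. It should not be read as an estimate for this study, and the documents do not show that any subject was misclassified. The primary negative binomial model and the main Cox model do not use Appendix 3. The change is still worth making because the rule is explicit, its weakness is visible on the page, and the repair is cheap.

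**What to change.** Before unblinding:

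1. In SAP 4.7.6.1, define any antibiotic by ATC class: systemic antibacterials (J01) plus inhaled antibacterials. Exclude topical, ophthalmic and otic use, and antifungals.
2. For drugs that carry more than one ATC code, review the individual records blind, using route where collected and otherwise reason for use. ATC summaries are planned in 4.6, but the SAP does not say that each record has one route-specific code, so this review is needed.
3. State how stable oral macrolides are counted, given that they are already a model term.
4. Keep Appendix 3 only for the anti-pseudomonal flag. Regenerate its terms from the coded data, check the three doubtful spellings against the dictionary, and remove AMPHOTERICIN B.

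The cost is SAP wording, one changed selection step in the program and a small blinded review of multi-route drugs. No new data or subjects are needed. After unblinding, the same change would have to be labelled post hoc under SAP section 1.
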